### 3.2 Secondary

- The frequency of unique subjects with: serious adverse events; adverse events leading to discontinuation; adverse events judged to be related to study drug/medication; Sheehan Suicidality Tracking Scale (S-STS) total score, clinically significant ECG and laboratory abnormalities that are observed during the randomization phase of the study.
- Change in Penn Facial Pain Scale-Revised total score from baseline to the end of the randomization phase of the study.
- Change in Pain Disability Index total score from baseline to the end of the randomization phase of the study.
- Patient Global Impression of Change Scale at the end of the randomization phase of the study.
- Patient daily recording of worst pain episode in a day as measured using the 11-point Numeric Pain Rating Scale.
- Achievement of at least a 2-point reduction in average daily Numeric Pain Rating Scale score.

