3.2 Estimands

An estimand is the target of estimation to address the scientific question of interest posed by a study objective. The 4 attributes of an estimand include the population of interest, endpoint of interest, specification of how intercurrent events are reflected in the scientific question of interest, and the summary for the endpoint.

For all objectives, the population of interest is defined through appropriate inclusion/exclusion criteria to reflect the targeted patient population for approval. Refer to the protocol for inclusion/exclusion criteria.

Intercurrent Events

Intercurrent events are those that occur after treatment initiation and either preclude observation of the endpoint or affect its interpretation. The following will be considered intercurrent events:

- Study drug discontinuation before the time point of interest defining the endpoint.
 - For safety objectives:
 - For AEs, study drug discontinuation is handled with a “while-on-treatment strategy,” i.e., response to treatment prior to the occurrence of the intercurrent event of interest, such that all observed values of the endpoint of interest will be used prior to study drug discontinuation.
 - For all other safety endpoints, study drug discontinuation is handled with a “treatment policy strategy”, i.e., the occurrence of the intercurrent event will be considered irrelevant, such that all observed values of the endpoint of interest will be used regardless of study drug discontinuation.
 - For efficacy objectives:
 - For the NPRS objectives, study drug discontinuation is handled with a “while-on-treatment strategy”.
 - For the Penn-FPS-R, PDI, and PGI-C efficacy objectives, study drug discontinuation is handled with a “treatment policy strategy”.
 - For all other objectives (i.e., use of non-study TN standard of care medications on or before the time point of interest), this intercurrent event will be handled with a “while-on-treatment strategy”

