3.2.2 Secondary Objective Estimands

Table 2 presents the estimands for secondary objectives.

Table 2: Secondary Objective Estimands

Objective 1	To assess the safety and tolerability of rimegepant relative to placebo in patients with TN
Safety Endpoint	Frequency of unique subjects with: SAEs, AEs leading to discontinuation, AEs judged to be related to study medication, S-STS total score, and clinically significant electrocardiogram (ECG) and laboratory abnormalities observed during the randomization phase of the study
Summary	Using the treated subjects population: 
Number and percentage of subjects with these events or findings
Intercurrent Events	Study drug discontinuation: while-on-treatment strategy for AEs; treatment policy strategy for all other safety endpoints
Objective 2	To evaluate the efficacy of rimegepant vs placebo for improving physical function in TN patients as measured by Penn-FPS-R
Efficacy Endpoint	Change in Penn-FPS-R total score from baseline to the end of the 2-week treatment phase of the study
Summary	Using the mITT population: 
Descriptive statistics for Penn-FPS-R and change from baseline as a continuous variable by treatment group at each visitDifference in mean change from baseline in Penn-FPS-R scores between treatment groups estimated using MMRM
Intercurrent Events	Study drug discontinuation: treatment policy strategy
Objective 3	To evaluate the efficacy of rimegepant vs placebo for improving functional disability in TN patients as measured by the Pain Disability Index
Efficacy Endpoint	Change in Pain Disability Index total score from baseline to the end of the 2-week treatment phase of the study
Summary	Using the mITT population: 
Descriptive statistics for Pain Disability Index and change from baseline as a continuous variable by treatment group at each visitDifference in mean change from baseline in Pain Disability Index between treatment groups estimated using MMRM
Intercurrent Events	Study drug discontinuation: treatment policy strategy
Objective 4	To evaluate the efficacy of rimegepant vs placebo on global functioning as measured by the PGI-C
Outcomes Research Endpoint	PGI-C Scale at the end of the 2-week treatment phase of the study

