6.4 Safety Analyses

Safety outcome measures include: AEs, laboratory assessments, vital signs, ECGs, concomitant medications, and the S-STS questionnaire.

Tables of safety endpoints are provided according to safety analysis period and analysis set as follows, unless otherwise noted:

- On-DBT for the DBT treated analysis set by treatment sequence and period, rimegepant pooled, and placebo pooled
- Post-DBT pre-OL rimegepant for the interim treated analysis set by treatment sequence and period, rimegepant pooled, placebo pooled, and overall
- On-OL rimegepant for the OL rimegepant treated analysis set by DB rimegepant pooled/OL rimegepant, DB placebo pooled/OL rimegepant, and overall. Shifts from baseline are based on the OL rimegepant baseline.
- On-DB or OL rimegepant for the DB or OL rimegepant treated analysis set by DB rimegepant pooled/OL rimegepant, DB placebo pooled/OL rimegepant, and overall. Shifts from baseline are based on the DB or OL rimegepant baseline.
- Follow-up for the follow-up treated analysis set by DB rimegepant pooled/OL rimegepant, DB placebo pooled/OL rimegepant, and overall.

6.4.1 *Adverse Events*

Refer to the Core SAP for the following: AE start and end date imputation; death date derivation; rules for counting and rounding in frequency tables; definitions of treatment-emergent adverse events (TEAEs), AEs related to study drug, and exposure-adjusted multiple occurrences of unique AEs; and TLF contents.

A by-subject AE listing is provided for the enrolled analysis set. TEAEs are identified.

6.4.1.1 *Deaths*

Deaths are identified from any of the following sources:

- AE CRF with any of the following: PT or reported term of “death”; outcome of fatal; “yes” response to any death-related question (e.g., “Did the SAE result in death?”; “Is a

death certificate available?"; "Is an autopsy report available?"); complete or partially complete death date

- Study Termination Summary CRF with any of the following: death as reason for discontinuation; complete or partially complete death date

The by-subject listing of deaths is provided for the enrolled analysis set.

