Vital signs will include systolic blood pressure, diastolic blood pressure, heart rate, temperature, and respiratory rate. In summaries, only vital signs measured in the sitting position will be included. Physical measurements will include height, weight and BMI.

6.4.3.1 *Vital Signs and Physical Measurements Changes From Baseline Over Time*

Values and changes from baseline in vital sign and physical measurement parameters will be summarized as continuous parameters at each scheduled visit.

The table of values and changes from baseline in vital signs and physical measurements is provided by rimegepant pooled, placebo pooled, and overall for the DBT treated analysis set at the following time points: baseline; each scheduled visit through Day 35 in the on-DBT safety analysis period; 2-week follow-up safety visit.

The table of values and changes from DB or OL rimegepant baseline in vital sign and physical measurement parameters is provided analogously for the DB or OL rimegepant treated analysis set at the following time points: DB or OL rimegepant baseline; each scheduled visit through Day 35 in the on-DBT safety analysis period; each scheduled visit from Day 63 through Day 119 and EOT in the on-OL rimegepant safety analysis period; and 2-week follow-up safety visit.

Refer to the Core SAP for handling multiple values in an analysis visit window or on the same measurement date, and deriving the EOT value in an on-treatment safety analysis period.

6.4.3.2 *Vital Signs and Physical Measurement Abnormalities*

Frequency tables of vital sign and physical measurement abnormalities are provided for the following safety analysis periods and analysis sets:

- On-DBT for the DBT treated analysis set
 - Summarized by rimegepant pooled, placebo pooled, and overall
- On-OL rimegepant for the OL rimegepant treated analysis set using OL rimegepant baseline
- On-DB or OL rimegepant for the DB or OL rimegepant treated analysis set using DB or OL rimegepant baseline

- Follow-up for the follow-up treated analysis set.

6.4.4 *Electrocardiograms*

12-Lead ECGs data will not be analyzed for the CSR.

6.4.5 *Sheehan-Suicidality Tracking Scale (S-STS)*

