7.2 Analysis Periods

Analysis periods are defined as follows:

- Efficacy endpoints
 - On-DBT efficacy: This period is used to assess efficacy during the DBT Phase, and is abbreviated as “DBT” in the efficacy listing.
 - On-OL rimegepant efficacy: This period is abbreviated as “OLRMG” and used only in the efficacy listing.
 - Follow-up efficacy: This period is abbreviated as “FU” and used in the efficacy listing.
- Pretreatment characteristics and safety endpoints
 - Pretreatment: This period is abbreviated as “PRETRT” in listings, and is used to derive baseline values and to assess pretreatment safety endpoints.
 - Pre-OL rimegepant: This period is used to derive the OL rimegepant baseline value.
 - Pre-DB or OL rimegepant: This period is used to derive the DB or OL rimegepant baseline value.
 - On-DBT safety: This period is abbreviated as “DBT” in safety listings, and is used to assess safety endpoints on DBT for the DBT treated analysis set
 - Post-DBT pre-OL rimegepant safety: This period is abbreviated as “INT” in safety listings, and is used to assess safety endpoints during the interim period (i.e., post-DBT pre-OL rimegepant) for the interim treated analysis set.
 - On-OL rimegepant safety: This period is abbreviated as “OLRMG” in safety listings, and is used to assess safety endpoints for the OL rimegepant treated analysis set.
 - On-DB or OL rimegepant safety: This period is used to assess safety endpoints on DB or OL rimegepant treatment for the DB or OL rimegepant treated analysis set
 - Follow-up safety: This period is abbreviated as “FU” in safety listings, and is used to assess safety endpoints during follow-up.
- Outcomes research endpoints
 - DBT outcomes research: This period is abbreviated as “DBT” in outcomes research listings, and used to assess outcomes research endpoints during the DBT Phase
 - OL rimegepant outcomes research: This period is abbreviated as “OLRMG” in outcomes research listings, and used to assess outcomes research endpoints during the OLE Phase.

For endpoints using the “treatment strategy policy”, analysis period 1 is defined as the Day 14 CRF visit, analysis period 2 is defined as the Day 35 or Day 35/ET CRF visit.

For endpoints using the “while-on-treatment strategy”:

- For AEs, refer to Section 6.4.1 for analysis period definitions.

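### SAP 6.4.4 drops ECG analysis while SAP Table 2 still promises a count of subjects with clinically significant ECG abnormalities

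*SAP*

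**What the plan says.** Protocol 3.2 includes in the secondary safety endpoint "clinically significant ECG and laboratory abnormalities that are observed during the randomization phase of the study". SAP Table 2 (section 3.2.2), Objective 1, carries this over as "clinically significant electrocardiogram (ECG) and laboratory abnormalities observed during the randomization phase of the study". For the treated population it specifies the summary "Number and percentage of subjects with these events or findings" and the intercurrent-event handling "while-on-treatment strategy for AEs; treatment policy strategy for all other safety endpoints". ECG is not an AE endpoint, so treatment policy applies. SAP 3.2 explains that as meaning "all observed values of the endpoint of interest will be used regardless of study drug discontinuation".

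SAP 6.4 opens with "Safety outcome measures include: AEs, laboratory assessments, vital signs, ECGs", followed by two further measures. It names ECGs only in general; the clinical-significance qualifier and the endpoint status come from Table 2.

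SAP 6.4.4, the whole of the ECG section, reads "12-Lead ECGs data will not be analyzed for the CSR".

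SAP 1 notes that the study was stopped early for low enrolment and that the CSR would therefore cover critical data only. SAP 8 says that every analysis the SAP describes is included.

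**The concern.** Table 2 describes an ECG analysis and 6.4.4 says there will be none. A programmer must break one of them. If 6.4.4 is followed, a declared component of secondary objective 1 has no by-treatment summary, although the ECGs are scheduled and collected. Nothing at the place where the endpoint is defined tells the reader so. Vital sign abnormalities, which are not in the Objective 1 endpoint, keep frequency tables in four safety periods (SAP 6.4.3.2). That does not show that ECG is critical data, but it does mean the reduced scope cannot be read off the endpoint definition.

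**Working it through.** No power or effect-size arithmetic applies. The check traces each Objective 1 component to its planned double-blind summary.

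| Component (SAP Table 2, Objective 1) | Planned summary | Match |
|---|---|---|
| SAEs | frequency table, 6.4.1.3 | direct |
| AEs leading to discontinuation | frequency table, 6.4.1.3 | direct |
| AEs related to study drug | frequency table, 6.4.1.3 | direct |
| Clinically significant laboratory abnormalities | worst toxicity grade and grade shift, 6.4.2.1 | loose (grade, not judged significance) |
| S-STS total score | scores and worst-change categories, 6.4.5 | loose |
| Clinically significant ECG abnormalities | none, 6.4.4 | none |

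Total: 3 direct + 2 loose + 1 none = 6. Five of six have a summary; ECG is the one that does not.

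**Could another text fill the gap?** The Core SAP governs only where this SAP is silent or refers to it (SAP 1). Section 6.4.4 addresses ECG and makes no such reference, so the Core SAP does not apply.

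**Do ECG findings appear elsewhere?** In two places, both indirect.
- SAP 9.1 counts QTc, bundle branch block and conduction-defect criteria as eligibility deviations, at pretreatment or at Day 35 for subjects entering the extension. SAP 6.2.4.1 tabulates these by sequence, so Day 14 is missed and treatments are not compared.
- Protocol 7 defines an AE broadly enough to cover a new ECG abnormality, and such events would reach the on-treatment AE tables, where cardiovascular AEs are of special interest. Protocol 8.3.2, however, lists which laboratory abnormalities must be captured on the AE or SAE form. No passage does this for ECG findings, so an AE count cannot stand in for the ECG component.

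**What data exist?** Protocol Table 1 schedules 4 ECGs in the double-blind phase (screening, baseline, Day 14, Day 35). Two are post-baseline, one per treatment period, and none is scheduled at Day 21. Protocol 5.2.2 adds ECGs when medically necessary. Table 1 footnote j lets procedures missed at a remote visit be done at the next visit, so a Day 14 ECG may fall at Day 21.

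**Do the existing period rules suffice?** Only partly. For treatment-policy endpoints, SAP 7.2 says "analysis period 1 is defined as the Day 14 CRF visit, analysis period 2 is defined as the Day 35" visit or its early-termination equivalent. Unscheduled and Day 21 ECGs have no period under that rule, yet treatment policy requires all observed values. A date rule is needed. SAP 6.4.1.3 already has one for AEs: the boundary between periods 1 and 2 is the first dose at the Day 21 visit.

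**The case against.** The strongest reply is that 6.4.4 is a stated scope decision. The study was terminated, the SAP limits the CSR to critical data, and the ECG sentence has the same form as the COVID-19 and PK exclusions (6.4.7, 6.5). A specific section would normally prevail over a carried-over table. Protocol 9.4.6, which lists the safety frequencies to be summarised, includes clinically relevant laboratory abnormalities but no ECG table, so the gap predates 6.4.4. SAP 5 also says that endpoint significance will not be evaluated, so no test is lost.

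Much of this stands. The omission is probably intended, and the loss is a descriptive count. But the termination note neither defines critical data nor names ECG, and COVID-19 impact and PK are not Objective 1 components. Nor is the estimand section simply untouched: the revision history says that version 2.0 updated section 3.2 with strategies for safety endpoints, and the ECG component remained. The missing entry in protocol 9.4.6 does not remove ECG from the endpoint in protocol 3.2.

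A reader might infer that ECG findings would vanish from the report. The documents do not support that, given the AE and deviation tables. A reader might also infer that a Day 14 and Day 35 count under 7.2 would be enough. It would leave out medically necessary and deferred ECGs, contrary to the all-observed-values rule.

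**Conclusion.** The point holds as a conflict between current passages. One of six components of the secondary safety endpoint has a promised summary in Table 2 and an explicit exclusion in 6.4.4, with no other safety or endpoint summary by treatment. It should be corrected. It does not touch the primary analysis, and the documents give no ground for inferring a hidden safety signal or an oversight rather than a scope cut.

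The conclusion rests on the protocol and SAP alone; the separate mock TLF document and the Core SAP were not available. Whether the case report form has a field for ECG clinical significance is unknown. The protocol summary names case report forms as a source for this endpoint but describes no such field.

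**What to change.** Replace 6.4.4 with the following.

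1. A by-subject listing of all ECGs.
2. If the case report form records the investigator's assessment of clinical significance, one frequency table for DBT treated subjects, rimegepant pooled versus placebo pooled, showing the number of subjects with an ECG in each period.
3. Under treatment policy, count every observed post-baseline ECG of the double-blind phase, including unscheduled, deferred Day 21 and early-termination ECGs.
4. Keep 7.2 for the Day 14 and Day 35 visits, and state a date-based assignment for the rest, for example the 6.4.1.3 boundary at the first Day 21 dose. Borrow only the boundary, not the AE cut-off of 7 days after last dose, which belongs to a while-on-treatment rule. Say how an ECG on the Day 21 visit date is placed if its time is not recorded.
5. Footnote ECGs taken in the placebo washout, which that boundary places in period 1. Also footnote ECGs of subjects who stopped in period 1: 7.2 would put a Day 35/ET ECG in period 2, whereas SAP 4.2 assesses treated subjects by treatment received.
6. If there is no significance field, provide the listing only, and label any threshold count post hoc.

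Alternatively, if the sponsor confirms that ECG is not critical data, mark the ECG component in Table 2 and in 6.4 as not analysed, give the reason, and disclose it in the CSR as a change from the protocol-specified endpoint.

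Cost: one table, one listing and one period-assignment rule, or text changes only for the alternative. Some Day 14 ECGs may be missing because protocol 3.5.2 allows that visit to be remote; how often is not stated.

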7 CONVENTIONS

7.1 *General*

7.1.1 *Output Layout*

Refer to the Core SAP for TLF layout conventions.

For the final analysis of the DBT phase and the final analysis after the OLE phase, a list of TLFs and unique TLF templates will be provided in the Mock TLF document.

7.2 Analysis Periods

Analysis periods are defined as follows:

- Efficacy endpoints
 - On-DBT efficacy: This period is used to assess efficacy during the DBT Phase, and is abbreviated as “DBT” in the efficacy listing.
 - On-OL rimegepant efficacy: This period is abbreviated as “OLRMG” and used only in the efficacy listing.
 - Follow-up efficacy: This period is abbreviated as “FU” and used in the efficacy listing.
- Pretreatment characteristics and safety endpoints
 - Pretreatment: This period is abbreviated as “PRETRT” in listings, and is used to derive baseline values and to assess pretreatment safety endpoints.
 - Pre-OL rimegepant: This period is used to derive the OL rimegepant baseline value.
 - Pre-DB or OL rimegepant: This period is used to derive the DB or OL rimegepant baseline value.
 - On-DBT safety: This period is abbreviated as “DBT” in safety listings, and is used to assess safety endpoints on DBT for the DBT treated analysis set
 - Post-DBT pre-OL rimegepant safety: This period is abbreviated as “INT” in safety listings, and is used to assess safety endpoints during the interim period (i.e., post-DBT pre-OL rimegepant) for the interim treated analysis set.
 - On-OL rimegepant safety: This period is abbreviated as “OLRMG” in safety listings, and is used to assess safety endpoints for the OL rimegepant treated analysis set.
 - On-DB or OL rimegepant safety: This period is used to assess safety endpoints on DB or OL rimegepant treatment for the DB or OL rimegepant treated analysis set
 - Follow-up safety: This period is abbreviated as “FU” in safety listings, and is used to assess safety endpoints during follow-up.
- Outcomes research endpoints
 - DBT outcomes research: This period is abbreviated as “DBT” in outcomes research listings, and used to assess outcomes research endpoints during the DBT Phase
 - OL rimegepant outcomes research: This period is abbreviated as “OLRMG” in outcomes research listings, and used to assess outcomes research endpoints during the OLE Phase.

For endpoints using the “treatment strategy policy”, analysis period 1 is defined as the Day 14 CRF visit, analysis period 2 is defined as the Day 35 or Day 35/ET CRF visit.

For endpoints using the “while-on-treatment strategy”:

- For AEs, refer to Section 6.4.1 for analysis period definitions.
- For NPRS endpoints, analysis period 1 is defined as the Day 14 visit, analysis period 2 is defined as the Day 35 or Day 35/ET visit, with visits derived using treatment exposure start and end dates.

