#### **5.2.8 Sheehan Suicidality Tracking Scale (Sheehan STS)**

The Sheehan STS is a prospective, patient self-reported or clinician administered rating scale that contains 16 questions to track both treatment-emergent suicidal ideation and behaviors. The S-STS will be completed on a paper form at the site. At the screening visit, the recall period for completing the S-STS is 30 days prior; at all other visits, the recall period for completing the S-STS is since the last visit. Subjects who have a S-STS score  $> 0$  should be immediately evaluated by the investigator. If the investigator determines that a subject is at risk of suicide or self-harm, appropriate measures to ensure the subject's safety and obtain mental health evaluation must be implemented. **The event should be recorded as either an AE or SAE determined by the investigator and reported within 24 hours to the Sponsor.** Subjects with a response of 1 ("a little") to Question 2 may be allowed in the study at the Screening and/or Baseline visits and eligible to continue participation in treatment phase. Investigator's review and assessment should be documented in subject source. Subjects with a response greater than 1 on Question 2 should not be enrolled in the study.

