6.4.1.3 On-DBT AEs

Frequency tables of on-DBT AEs are provided for the DBT treated analysis set by SOC and PT for the following endpoints:

- AEs by intensity
- AEs related to study drug by intensity
- AEs by relationship to study drug (related, possibly related, unlikely related, not related, not reported)
- SAEs
- AEs leading to study drug discontinuation
- Exposure-adjusted multiple occurrences of unique AEs
- Hepatic-related AEs by intensity *
- Cardiovascular AEs *
- Suicidality AEs *.

AEs of special interest are asterisked ("*").

AEs with a start date on or after the first dose date/time on the Day 1 visit and prior to the first dose date/time on the Day 21 visit is considered to be in the on-DBT analysis period 1. AEs with a start date on or after the first dose date/time on the Day 21 visit to the earlier of the last dose of the DBT + 7 or the first dose of OLE - 1 is considered to be in the on-DBT analysis period 2.

Calculations for on-DB rimegepant exposure-adjusted multiple occurrences of unique AEs use an analysis period reference start date = DB rimegepant start date, analysis period reference end date = DB rimegepant last date + 7 days.

6.4.1.4 *On-OL Rimegepant AEs*

Frequency tables of on-OL rimegepant AEs are provided for the OL rimegepant treated analysis set by SOC and PT for the following endpoints:

- AEs by intensity
- AEs related to study drug by intensity
- AEs by relationship to study drug (related, possibly related, unlikely related, not related, not reported)
- SAEs
- AEs leading to study drug discontinuation

AEs with a start date on or after the first dose date/time of OL rimegepant and prior to the last dose date of the OL rimegepant + 7 is considered to be in the on-OL analysis period.

6.4.1.5 *On-DB or OL Rimegepant AEs*

On-DB or OL rimegepant AEs are provided for the DB or OL rimegepant treated analysis set by SOC and PT for the same endpoints listed in Section [6.4.1.3](#).

AEs with a start date on or after the first dose date/time of DB rimegepant or OL rimegepant and prior to the last dose date of the DB or OL rimegepant + 7 is considered to be in the on-DB or OL rimegepant analysis period.

Calculations for on-DB or on-OL rimegepant exposure-adjusted multiple occurrences of unique AEs use an analysis period reference start date = DB or OL rimegepant start date, analysis period reference end date = DB or OL rimegepant last date + 7 days.

6.4.1.6 *Post-DBT Pre-OL Rimegepant AEs*

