The S-STS is a prospective rating scale that contains 16 patient-reported questions and 6 clinician-reported questions to track both treatment-emergent suicidal ideation and behaviors. The S-STS will be assessed at early termination and the following visits: Screening, Baseline (Day 1), Day 14, Day 21, Day 35, Day 63, Day 91, Day 119/EOT, and 2-week follow-up safety visit.

S-STS scores are calculated as described in the Core SAP.

Values and changes from baseline in the self-reported S-STS ideation subscale, behavior subscale, and total score will be summarized as continuous parameters at baseline and the worst (highest) score by rimegepant pooled, placebo pooled and overall.

In addition, the number and percentage of subjects in the worst (highest) score change from baseline category (i.e., < -1, -1, no change, 1, > 1) will also be presented by rimegepant pooled, placebo pooled and overall for the ideation subscale, behavior subscale, and total score.

S-STS scores, worst score changes from baseline, and worst score change categories from baseline will be summarized for the following safety analysis periods and populations: (1) on-DBT for treated subjects; (2) on-OL rimegepant for OL rimegepant treated subject; (3) on-DB or OL rimegepant for DB or OL rimegepant treated subjects, using DB or OL rimegepant baseline; and (4) follow-up for follow-up treated subjects.

6.4.6 *Concomitant Procedures*

The by-subject listing of procedures is provided for the enrolled analysis set, and is based on the Concomitant Procedures CRF. Procedures are coded in MedDRA. Refer to the Core SAP for additional details.

6.4.7 *Covid-19 Impact*

Covid-19 impact will not be assessed for this CSR.

6.5 *Pharmacokinetics*

PK will not be analyzed for this CSR.

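### SAP 7.2, read with SAP 3.2, gives the Day 21 S-STS no treatment column in the worst-score tables, so on schedule the washout week is missing from the by-treatment comparison

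*SAP*

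**What the plan says.** SAP 3.2 splits the safety endpoints by strategy. Adverse events (AEs) are handled while on treatment. For the rest it states: "For all other safety endpoints, study drug discontinuation is handled with a" treatment policy strategy. SAP Table 2 (section 3.2.2) confirms that the S-STS is among the rest. Its Objective 1 safety endpoint lists "AEs judged to be related to study medication, S-STS total score, and clinically significant electrocardiogram (ECG) and laboratory abnormalities", and its intercurrent-event row reads "while-on-treatment strategy for AEs; treatment policy strategy for all other safety endpoints".

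SAP 7.2 then fixes the analysis periods for endpoints under that strategy: "analysis period 1 is defined as the Day 14 CRF visit, analysis period 2 is defined as the Day 35" or Day 35/ET visit.

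SAP 6.4.5 schedules the S-STS at Day 14, Day 21 and Day 35 in the double-blind phase, as does protocol Table 1. Scores are "summarized as continuous parameters at baseline and the worst (highest) score by rimegepant pooled, placebo pooled and overall", with worst changes and change categories shown the same way for the on-DBT (double-blind treatment) safety period. Protocol 5.2.8 sets the recall: after screening, "at all other visits, the recall period for completing the S-STS is since the last visit".

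Two other parts of the SAP treat the washout week differently. For AEs, section 6.4.1.3 says that an event starting from the first Day 1 dose and "prior to the first dose date/time on the Day 21 visit is considered to be in the on-DBT analysis period 1". For vital signs, also a treatment-policy endpoint, section 6.4.3.1 tabulates every scheduled visit through Day 35 by pooled rimegepant and pooled placebo, which includes Day 21.

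**The concern.** In a crossover, an assessment reaches a treatment column only through the period to which it is assigned. A form with no period therefore has no treatment. The Day 21 S-STS is in that position under 7.2, and on schedule no other form can stand in for it, because the Day 35 form looks back only to Day 21.

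The washout week is the only part of the double-blind phase in which patients who have just stopped rimegepant can be compared, under blinding, with patients who had taken placebo throughout. Suicidality in that week is worth seeing by treatment. The S-STS total score is named in the secondary safety endpoint, and its analysis was kept when the plan was cut back after early termination, whereas ECG and pharmacokinetic analyses were dropped. The study has no data monitoring committee (protocol 10.2).

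The practical risk is a pair of tables that do not line up: a suicidality AE in washout is counted to period 1, while the S-STS score recorded for the same days reaches neither treatment column.

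**Working it through.** There is no planned figure to reproduce. The check is a cross-reading followed by a count.

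**Does Day 21 have a period?**

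| Source | Endpoint | Where Day 21 or the washout week goes |
|---|---|---|
| SAP 7.2 with 3.2 | S-STS and other treatment-policy endpoints | Neither period 1 (Day 14) nor period 2 (Day 35 or Day 35/ET) |
| SAP 6.4.1.3 | AEs | Period 1, up to the first dose at the Day 21 visit |
| SAP 6.4.3.1 | Vital signs | Tabulated by pooled treatment, with no stated rule for the treatment to which Day 21 belongs |

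Section 7.2 transposes the words of the strategy name; I read it as the treatment policy strategy of 3.2, since no other strategy fits.

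**How much is left out of the treatment columns?** Inputs are the nominal visit days (protocol Table 1), the 7-day washout (protocol 3.5.2) and the recall rule (protocol 5.2.8).

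- Recall by form: Day 14 covers 14 days, Day 21 covers 21 − 14 = 7 days, and Day 35 covers 35 − 21 = 14 days. The total is 14 + 7 + 14 = 35.
- Without Day 21: 14 + 14 = 28 of 35 days are covered. The gap is 7/35 = 20% of the double-blind phase, or 7/21 = 33% of the AE period 1.
- Forms per patient: 2 of 3 kept, 1 of 3 left out.
- At the planned 60 patients, all completing: 3 × 60 = 180 forms, 60 left out. With 20% dropout, 60 × 0.8 = 48 completers: 3 × 48 = 144 forms, 48 left out. Actual numbers will differ because enrollment stopped early.
- Scheduled forms per period: one in each. A worst score by treatment then has nothing to choose from unless there is an unscheduled form.

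**How many of those forms follow rimegepant?** With 1:1 randomization, 60/2 = 30 patients are rimegepant-first. Only their Day 21 forms follow a switch from rimegepant to placebo. The other 30 record placebo after placebo.

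**Which way does the omission push the comparison?** For any patient, a maximum over fewer forms is equal or lower. If Day 21 belongs to period 1, it goes to the rimegepant column for rimegepant-first patients and to the placebo column for placebo-first patients. Both columns lose forms, so the effect on the difference between them has no known sign.

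**After assigning Day 21 to period 1:** 3 of 3 forms and 35 of 35 days are used. Period 1 has two scheduled forms and period 2 has one. Each pooled column receives 30 × 2 + 30 × 1 = 90 forms at the planned size, so the columns stay balanced.

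**The case against.** The strongest reply is that 6.4.5 never meant to exclude Day 21. It lists Day 21 as an S-STS visit and takes the worst score over the on-DBT safety period, which 7.2 names separately from periods 1 and 2. A worst score makes little sense with one form per treatment, and the vital signs table shows that Day 21 is not barred from safety tables. The Day 14/Day 35 sentence was probably written for Penn-FPS-R, Pain Disability Index and PGI-C. That is a fair guess at intent, and it is why Day 21 may well survive in the overall column. It still does not tell a programmer which treatment column the form enters, and the rule as written covers all endpoints under the strategy.

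The Core SAP, not available here, might settle attribution. By SAP section 1 it takes precedence only where this SAP is silent or refers to it directly. Section 7.2 is not silent on periods, and 6.4.5 sends only the S-STS score calculation to the Core SAP.

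The signal also has other routes. Protocol 5.2.8 requires the investigator to evaluate any S-STS score above 0 and to record an event of suicide or self-harm risk as an AE or SAE. Suicidality AEs are tabulated with washout in period 1. SAP 9.1 lists threshold S-STS scores at any visit as relevant deviations, though the heading above that item is narrower. This stands: a washout event need not go unseen. It does not restore the by-treatment score comparison.

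Two further points stand in part. AEs and S-STS are under different strategies by design, so their tables need not match. And assigning Day 21 to period 1 credits placebo days to rimegepant in one sequence; since Day 21 is also the start-of-period-2 assessment (protocol 3.5.2), a separate washout row is defensible.

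**Conclusion.** The point holds as a gap between sections of the SAP. Followed literally, 3.2 and 7.2 leave the Day 21 S-STS without a treatment column in the 6.4.5 worst-score tables: 1 of 3 post-baseline double-blind forms and 7 of 35 days, at nominal visit days and with the Day 21 visit attended. If that visit is missed, the Day 35 recall reaches back to Day 14.

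Three stronger readings are not supported:

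- A reader might infer that all non-AE safety endpoints lose Day 21. Vital signs at Day 21 are tabulated by pooled treatment, laboratory tests are not scheduled then, and ECGs are not analysed.
- A reader might infer that the form is discarded altogether. The on-DBT safety period has no dates in 7.2, so Day 21 may remain in the overall column.
- A reader might infer that rimegepant would look safer. Both treatment columns lose forms and the direction is unknown; all that can be said is that a worsening after stopping rimegepant, in the rimegepant-first sequence, could be absent from this table.

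The table is descriptive, and SAP section 5 rules out significance evaluation, so no formal conclusion turns on this. It should still be corrected, because it concerns a suicidality measure already collected and the rule is explicit enough to be programmed as it stands.

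**What to change.** In SAP 7.2, restrict the Day 14 / Day 35 or Day 35/ET definition to Penn-FPS-R, Pain Disability Index and PGI-C. Add that the Day 21 S-STS, and any unscheduled S-STS before the first period-2 dose, belongs to analysis period 1, in line with 6.4.1.3. In the 6.4.5 tables, footnote worst scores that came from the washout visit, or also show them in a separate washout row.

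The cost is a short text change and a footnote or row; no new data are needed. The small downside is that period 1 for the S-STS then includes a placebo week, as the AE table already does. The footnote or row lets the reader separate the two.
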